1 INTRODUCTION

1.1 Study Overview

Title	ATG-GCSF in New Onset Type 1 Diabetes
IND Sponsor	National Institute of Diabetes and Digestive and Kidney Diseases (NIDDK)
Conducted By	Type 1 Diabetes Trial Network (TrialNet)
Protocol Chair	[name]
Accrual Objective	84
Study Design	Three-arm, 1:1:1 randomized, placebo controlled, double-blinded trial in which at least 28 subjects will receive active ATG-GCSF, at least 28 subjects will receive ATG alone and at least 28 subjects will receive placebo alone within 100 days from diagnosis of T1D. An adaptive design will be used to determine the variance of C-peptide over time and may require additional subjects to be enrolled in each group to preserve power.
Treatment Description	ATG will be administered at a dose of 2.5mg/kg as two divided IV infusions of 0.5mg/kg and 2mg/kg. GCSF will be administered at a dose of 6mg SC or if <44.5 kg a dose of 100 mcg/kg every two weeks for a total of 6 doses.
Study Duration	Enrollment is expected to occur over two-three years. Subjects will be followed up to 24 months from randomization in this protocol.
Objective	To determine the safety and ability of low dose ATG plus GCSF and low dose ATG alone to retain/enhance C-peptide production in new onset T1D patients demonstrating residual beta cell function.
Primary Outcome	The primary statistical hypothesis to be assessed in the study is whether the 2 hour area under the curve (change in baseline to 12 months) in residual beta cell function (C-peptide) will differ between those treated with ATG and GCSF or ATG alone as compared with placebo.
Secondary Goals	The study will also examine the effect of the proposed treatments on surrogate markers for immunologic and metabolic outcomes
Major Inclusion Criteria	Type 1 diabetes diagnosed within the past 100 days Age \geq 12 years < 46 At least one diabetes associated autoantibody

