3.2 Description of Treatment Groups

This protocol will enroll at least 84 participants who will be randomly assigned to the following groups:

- 28 participants will be assigned to receive ATG + GCSF
- 28 participants will be assigned to receive ATG + Placebo
- 28 participants will be assigned to receive Placebo + Placebo

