8.4 Sample Size and Power Calculations

The primary analysis will compare the difference in C-Peptide between experimental and placebo treatment groups at 12 months using $\log(Y_{Cp} + 1)$ transformation and ANCOVA model adjusting for gender, baseline age and the baseline value of $\log(Y_{Cp} + 1)$. Estimates of the mean and standard deviation of $\log(Y_{Cp} + 1)$ (expressed algebraically as: $\hat{\mu}_{\log(Y_{Cp} + 1)}$ and $\hat{\sigma}_{\log(Y_{Cp} + 1)}$) in the placebo group were derived from the last four TrialNet studies of early onset disease. The 90% confidence bound estimates were used to provide good confidence that this trial's study population characteristics fall within these limits to assure the advertised statistical power; the estimates are $\hat{\mu}_{\log(Y_{Cp} + 1)} = 0.360$ and $\hat{\sigma}_{\log(Y_{Cp} + 1)|X} = 0.167$ (i.e., the residual mean squared error regressing on gender, baseline age and C-peptide). The geometric-like mean of Y_{Cp} for the placebo group is $\exp(0.36) - 1 = 0.433$ nmol/L.

Using standard equations for the comparison of two means and a 1:1:1 allocation, a sample size of 78 participants (26 per group) with complete data would provide power of 85% to detect a 50% increase in the geometric-like mean in either experimental treatment group (compared to the control) using the Wald test (from the adjusted linear model) at the 0.025 level (one-sided). Thus the overall Type I error for both tests is approximately 0.05.

Assuming that 10% of the participants will have missing data (one-year MMTT was not done or subject withdrew prior to the one-year assessment), the sample size goal for this study will be set at 84 participants (28 per group).

The study will be closed to additional participants when the total number then randomized plus a fraction of those in screening (i.e., screening for eligibility) is expected to provide the proper number of eligible participants. Participants who had already conducted the initial screening visit at that time will be allowed to complete screening and be randomized if both consenting and eligible.

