8.5 Sample Size Re-estimation

The Residual Mean Square Error (RMSE) and the mean of the control group are two parameters used in determining the sample size goal ($N_{SSG}=78$) which are directly tied to the study cohort enrolled. The former value is directly proportional to the sample size and the latter applies its influence in defining the effect size. Thus the advertised statistical power of this trial may differ from the actual power if either differs from the initial values assumed. Consequently, the plan is to estimate both values using the accumulated data (internal interim estimate, IIE) when approximately half the subjects ($N_{SSG}/2$) have had their 1 year C-Peptide assessment. Since the initial values used are based on real data from four previous TrialNet studies, the re-estimation of each parameter will be a two-term weighted average using the number of subjects on which the IIE is based as the one weight (N_{IIE}) and the remaining number of subjects participants to be enrolled as the other weight ($N_{SSG}-N_{IIE}$). Algebraically, the re-estimate will be computed:

$$\hat{\sigma}_{Re-estimate}^2 = \frac{N_{IIE}\hat{\sigma}_{IIE}^2 + (N_{SSG} - N_{IIE})\hat{\sigma}_{Initial}^2}{N_{SSG}}$$

Similarly, re-estimation of the mean of the control group will be calculated. These new estimates will be used to calculate a new sample size goal for the trial.

It is important to note that this adaptive procedure is a non-comparative interim analysis (i.e., the observed treatment effect has no influence on the sample size re-estimation). Therefore, this analysis has no effect on the type I error. Note the re-estimation can be conducted by the analyst in a blinded fashion. The goal is to assure adequate statistical power at the completion

of the trial by assuring the two design parameters reflect accurately the study population being enrolled.

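### Sections 1.1 and 3.2 commit to at least 84 participants, but the re-estimation rule in 8.5 can lower the goal and states no floor (minor)

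*Protocol*

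**What the plan says.** - **Protocol 1.1 (Study Overview)** gives a minimum of 28 per arm. It says the adaptive design will determine the variance of C-peptide and "may require additional subjects to be enrolled in each group to preserve power". A decrease is not mentioned.
- **Protocol 3.2**: "This protocol will enroll at least 84 participants who will be randomly assigned to the following groups", followed by three groups of 28. This section does not mention re-estimation.
- **Protocol 8.4** derives 78 participants with complete data (26 per group), which "would provide power of 85% to detect a 50% increase in the geometric-like mean in either experimental treatment group". It raises this to 84 randomised for missing data. On the planning values it says "The 90% confidence bound estimates were used to provide good confidence". Accrual closes once the randomised total, plus a share of those in screening, is expected to supply the number needed.
- **Protocol 8.5** takes the residual variance and the control-group mean when about half of the 78 have one-year results. It averages each with its planning value, weighting by numbers of participants. Then: "These new estimates will be used to calculate a new sample size goal for the trial". No minimum, maximum or increase-only condition is given, and nothing refers back to 1.1 or 3.2.

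**The concern.** The formula in 8.5 is symmetric. An interim variance below the planning value, or an interim control mean above it, gives a goal below 78. Sections 1.1 and 3.2 exclude that result, so an analyst who applies 8.5 literally and a reader who relies on 1.1 would expect different trials.

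The interim estimates are also noisy. The variance rests on about 39 participants and the control mean on about 13, so a lower goal can come from chance alone. Where it does, the trial ends with less than the stated power, although 8.5 gives adequate power as its purpose.

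**Working it through.** **Inputs from Protocol 8.4 and 8.5.** One-sided 0.025 per comparison; power 85%; control mean m = 0.360 and residual SD s = 0.167 on the log(Y+1) scale; 50% increase in the geometric-like mean; 1:1:1 allocation; goal 78 complete; re-estimation at about 39 one-year results, so weights of 39/78 on the interim and planning values.

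**Assumptions not in the protocol.** 13 controls at the look; about 33 residual df; marginal SD of the control group 0.167 to 0.25; even accrual.

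**Step 1: reproduce 78.**
- Effect: d = ln(1 + 1.5(e^m − 1)) − m = ln(1 + 1.5 × 0.433) − 0.360 = 0.1408.
- n per arm = 2(1.960 + 1.036)² s²/d² = 2 × 8.978 × 0.02789/0.01982 = 25.3, rounded up to 26, so 78 in total. The plan's figure reproduces.
- Power at 26 per arm is 85.0% by the noncentral t and 86.0% by the normal approximation.

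**Step 2: one pass through the 8.5 rule.**
- Interim residual SD 0.15: averaged variance = (0.0225 + 0.02789)/2 = 0.02519; n = 22.8, rounded up to 23 per arm, goal 69.
- If the interim control mean is also 0.40: averaged mean = (0.40 + 0.36)/2 = 0.38, d = 0.1468, n = 21.01, rounded up to 22 per arm, goal 66.
- If the planning values are in fact true, power is 80.4% at 69 complete and 78.5% at 66.

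**Step 3: simulate the rule with the planning values exactly true.** The interim variance is drawn as s² × χ²(df)/df and the control mean with SE = SD/√13.

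| Quantity | Variance only | Variance and control mean |
|---|---|---|
| Goal below 78 | 49-50% of runs | 49% |
| 5th to 95th percentile of goal | 63 to 93 | about 57-60 to 99-108 |
| Mean goal when cut | – | about 67-68 |
| Power in the cut runs | – | about 79-80% |
| Power over all runs, no floor | – | about 84% |
| Power over all runs, floor at 78 | – | about 87% |

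The power rows use the noncentral t. With the normal approximation, power over all runs without a floor is about 85%.

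**Step 4: vary the truth and the method.**
- Truth better than the planning values (illustration: SD 0.157, mean 0.38): the goal is cut in 70-74% of runs, but power in the cut runs is about 85% and over all runs about 87.5%.
- Variance estimated blinded with the arms lumped, and a true design effect in one or both active arms: the goal is cut in about 26% of runs.

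**Step 5: room left to cut.** Protocol 1.1 expects two to three years of accrual.
- Three years: 84/36 = 2.33 per month. With 10% missing, 39 results need 39/0.9 = 43.3 randomised, reached at month 18.6. One year later, at month 30.6, 30.6 × 2.33 = about 71 are randomised.
- Two years: 84/24 = 3.5 per month. On the same basis the look comes at month 24.4, when all 84 are randomised. With no missing data it comes at month 23.1, with 81 randomised.
- A mean cut goal of 68 complete is 68/0.9 = about 76 randomised, roughly 8 fewer than 84.

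**The case against.** **The minimum in 1.1 and 3.2 may already be the floor.** Section 1.1 describes the same adaptive procedure, 8.5 never says the goal may fall, and the closing rule in 8.4 reads as a provision for people still in screening. On that reading only a cross-reference is missing. This is fair, and the word "only" is indeed not in 1.1: that re-estimation can only add is an inference from the minimum and the mention of additional subjects. But 8.5 gives an explicit formula whose output can contradict that minimum, so the sections still have to be reconciled.

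**A two-way rule is legitimate.** Runs that are cut are offset by runs that gain participants, and the average power stays close to 85%. The equal weight on cautious planning values is itself a protection. This stands as a comment on design choice and is why the harm is small. It does not make the two-way rule agree with 1.1 and 3.2.

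**Stronger readings that the documents do not support.**
- A reader might infer that, because the planning values are 90% bounds, cuts will be usual and power will usually be lost. Cuts do become more frequent when the truth is better than the bounds, but power in those runs stays near 85%. The loss arises when the truth lies at the cautious bound.
- A reader might combine 67 randomised at the look with 10% missing data and arrive at 60 complete and about 75% power. The 67 assumes no missing data. With 10% missing about 71 are already randomised, so that figure should not be used.
- A reader might quote the one-half figure without conditions. It needs an arm-adjusted variance. That is the natural reading, since 8.5 also re-estimates the control-group mean, but 8.5 allows blinded re-estimation.

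**Conclusion.** The inconsistency is in the text and holds: 1.1 and 3.2 set a minimum of 84, while the rule in 8.5 can produce a lower goal. With the planning values true and the variance adjusted for arm, this happens in about half of runs. The cost there is about 5 to 6 points of power in the runs that are cut and about 1 point on average.

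These sizes rest on the assumed 39 results, 13 controls and 33 df. They shrink if the population is more favourable than planned, if the variance is taken blinded across arms while a real effect exists, or if accrual is fast. With three-year accrual about 13 of the 84 places remain open at the look; with two-year accrual there are almost none. Severity: minor.

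**What to change.** Add one sentence to Protocol 8.5, for example: *The re-estimated goal will not be lower than 78 participants with complete data (84 randomised); re-estimation can only increase the sample size.* This brings 8.5 into agreement with 1.1 and 3.2, and uses the protocol's own pairing of 78 complete with 84 randomised.

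The floor requires no participants beyond the 84 already promised and no new analysis. Increases above 78 remain possible, as now. The small downside is giving up the option to end accrual early when the variance is low, an option that 1.1 and 3.2 do not offer.

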2 BACKGROUND AND SIGNIFICANCE

2.1 Introduction

Recent advances in our understanding of the pathogenesis of T1D have been somewhat overshadowed by our continued inability to develop a long lasting means to either reverse or prevent the disease (i.e., identify a cure), using a variety of interventions (e.g., cyclosporine, anti-CD3, anti-CD20, oral insulin) (1-3). The majority of attempts to reverse T1D in humans have, to date, involved the delivery of agents as monotherapy. As a result, we and others have recently questioned whether the delivery of therapeutics in combination might produce a synergistic response that would allow for the successful reversal of T1D (2, 3). The success of combination therapy for advancing the treatment of patients with HIV and cancer demonstrates a model for multi-agent therapy in diseases involving multiple pathways required for their successful treatment and cure.

As described below, based on strong preliminary data demonstrating efficacy and potential mechanisms leading to reversal of diabetes in NOD mice with a combination of ATG and GCSF, as well as preliminary safety and efficacy studies in humans with T1D utilizing ATG and GCSF as monotherapies and in combination, we will test the hypothesis that a short course of low dose ATG or a combination of low dose ATG plus GCSF will lead to preservation of C-peptide in patients with new onset T1D.

2.2 ATG Monotherapy

2.2.1 *Rationale for ATG Therapy in T1D*

Preclinical studies have shown that ALS treatment of the NOD mouse (18) and BB rat (19) with recent onset T1D can induce remission, supporting proof of principle for such an approach in humans. The case for combination of ATG with other agents received support from follow-up studies in new-onset NOD mice involving the addition of Exendin-4, a long-acting GLP-1 agonist shown to augment insulin secretion in rodents (22) as well as T1D (23) and T2D (24) subjects, where remissions were seen in 90% of combination treated mice. While our own NOD studies (Preliminary Data section) found ATG and GCSF to be a superior combination (in comparison to ALS and Exendin-4) both sets of data provide additional support for the concept of combination therapy and its superiority to relatively ineffective monotherapy in terms of reversing T1D.

As further proof of the potential for translation from mouse to man, studies in human transplantation and various autoimmune conditions suggest that ATG may indeed induce tolerance. ATG has been successfully used as combination therapy in preventing rejection following organ transplantation. After induction with ATG, transplant recipients can be managed successfully with only limited maintenance monotherapy (25, 26), with weaning of some to as little as a single dose of tacrolimus per week. ATG, either alone or in combination with other agents, has also been used to treat a variety of autoimmune conditions, including Wegner's granulomatosis, lupus, rheumatoid arthritis, multiple sclerosis, scleroderma, aplastic anemia and myelodysplastic syndrome; with greater efficacy observed when used in combination (27-38). Extensive studies with ATG in a non-human primate model demonstrates its effectiveness as a single agent in T-cell depletion intravascularly and in peripheral lymphoid organs, as well as in prolongation of allograft transplantation of skin and heart (39).

Other studies also support ATG's possible efficacy in T1D. Specifically, early limited human studies with equine ATG and prednisone with new onset T1D suggested efficacy in prolonging

the honeymoon phase (11, 40). In a small randomized, placebo-controlled, single-blinded trial with ATG (ATG-Fresenius, Germany), T1D participants aged 18-35 years received a total dose of 18 mg/kg of ATG, administered in four infusions. Of the 17 study participants treated, 11 received drug while 6 received placebo. In terms of efficacy, increased glucagon-stimulated C-peptide levels, a lower insulin requirement, and lower glycosylated hemoglobin levels were reported in the ATG group (but not placebo group) at the 12 month study visit. Perhaps most promising, two ATG treated subjects achieved remission (i.e., off exogenous insulin for at least 1 month with fasting blood glucose below 126 mg/dl). (41).

Recently, a phase 2 study in humans with new-onset T1D and funded by the Immune Tolerance Network (ITN) was completed to determine if ATG (6.5mg/kg) could preserve C-peptide in new onset T1D. The study tested the hypothesis that selective deletion of lymphocytes would reset the immunologic rheostat, effect dynamic immune regulation and perhaps induce and maintain tolerance in T1D. While this study helped to establish the relative safety of ATG in humans with T1D, the study failed to demonstrate benefit (41b). Post-hoc analyses have suggested that an initial decline in beta cell function amongst those who were treated with active drug was followed by a relative preservation of beta cell function. We hypothesize that the initial decline in beta cell function was related to the severity of cytokine release syndrome and serum sickness. Furthermore, we hypothesize that the currently proposed protocol (utilizing ~1/3 of the ATG dose in combination with GCSF) will result in less severe cytokine release/serum sickness and, as is supported by our preliminary data, preservation/improvement in beta cell function 12 months after therapy.

2.2.2 Potential Mechanism of Action

ATG appears to induce both generalized immunosuppression and immunoregulation, with effects on APC and immunoregulatory cell function (42). It prevents B-cell proliferation and differentiation, as well as mediates T-cell suppressive effects via inhibition of proliferative responses to mitogens (43, 44). A single “typical” or “standard” dose of ATG reduces the total lymphocyte count by more than 85%. T-cell depletion may result from complement-dependent opsonization and cellular lysis, Fc-dependent opsonization, or Fas-mediated apoptosis; particularly at lower ATG concentrations, at which ATG exhibits preferential effects on pre-activated, as opposed to nonactivated, T-cells. T-cell depletion in peripheral blood persists for several days to several months following cessation of ATG administration. Recovery from treatment-induced lymphocyte depletion is gradual and total lymphocyte counts usually return to normal with 2 months after ATG administration.

Following ATG function, the CD4:CD8 T cell ratio remains significantly and persistently lower and the ratio may correlate with the outcome in transplantation studies (45-48). It has been hypothesized that ATG administration may induce a regulatory population of CD8+, CD57+ and CD28- cells that is critical for selective down regulation of pathogenic self-reactive CD4+ Th1 cells and the induction of tolerance.

Other studies have suggested alternative mechanisms to underlie the beneficial effects of ATG in vivo. As with anti-CD3, ATG may induce partial T-cell activation, leading to an anergic state (39, 53, 54). In cynomolgus monkeys, ATG appears to coat T cells, leading to a down regulation in surface expression of CD2, CD3, CD4, and CD8 molecules, along with impaired immune responses in mixed lymphocyte reactions (39). In addition, antibodies to adhesion molecules may interfere with cellular adhesion and endothelial interactions, as well as T-cell migration to sites of inflammation. ATG may also prevent co-stimulation of T cells by binding directly to APC, and may induce complement-mediated lysis of these cells; particularly in more mature APC (55). The survival of immature DC thus may be more tolerogenic. Antigens recognized by ATG

include CD86, CD32, CD4, CD11b, CD29, and CD51/61; some of which are shared by lymphocytes and DC. In addition, ATG contains antibodies that cross-react with B-cell surface antigens, allowing for induction of activated B-cell (another source of APC) apoptosis in vitro (56-58).

2.3 Granulocyte colony-stimulating factor (GCSF) monotherapy

2.3.1 Rationale for GCSF Therapy in T1D

In a spontaneous diabetes model, GCSF treatment of NOD mice at 4 weeks of age for 5 consecutive days, repeated every 4 weeks thereafter until 16 weeks of age, prevented disease onset and insulinitis when compared to injection of excipient (Figure 2) (59). Protection from diabetes onset correlated with the recruitment of both DC and CD4+CD25+ Treg cells. Indeed, the GCSF recipients showed peri-pancreatic lymph node accumulation of functional CD4+CD25+ Treg cells (60). Importantly, co-transfer of the functional Treg populations along with diabetogenic splenocytes into secondary NOD-SCID recipients actively suppressed diabetes. In addition, DC transferred from mice given a single 5-day-long GCSF treatment to secondary NOD recipients triggered enhanced accumulation of CD4+CD25+ Treg cells compared to recipients given non-GCSF treated DC. Thus, GCSF likely restores a balance between immunogenic and tolerogenic DC, resulting in the recruitment of functional CD4+CD25+ Treg cells.

Based on supportive data from animal models, several groups have moved on to initiate clinical trials of GCSF based therapies in human autoimmune disease. Perhaps the most extensive human data derives from studies of GCSF therapy in patients with Crohn disease. Several studies have now demonstrated improvement in clinical disease scores in patients with Crohn disease provided varying courses of GCSF (61-62). Specifically, a 12 week course of 300mcg daily GCSF, demonstrated marked reduction in the Crohn Disease Activity Index amongst 15 subjects with active disease (62). In a smaller study of Crohn disease patients with a history of severe endoscopic ileitis, a similar 12-week course of GCSF was associated with clinical remission of disease in all 5 subjects (61).

